### Sexual risk-taking behavior

Exploratory statistics will be used to explore and summarize sexual risk-taking behavior collected via ACASI. Summary plots will be produced for longitudinal changes in sexual risk-taking behavior among study participants.

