### **2.2 Secondary Objectives**

The secondary objectives of this study are:

- To determine annual incidence of HIV infection among study participants.
- To determine baseline prevalence and annual incidence of STIs (*Neisseria gonorrhoeae* [GC], *Chlamydia trachomatis* [CT], and *Treponema pallidum* (syphilis)) and to examine changes in STI incidence over time by study arm.

- To examine changes in sexual risk-taking behavior (e.g., number of serodiscordant or HIV-unknown serostatus sexual partners; number of condomless anal/vaginal sex episodes with these partners).
- To obtain baseline laboratory data to evaluate the cohort's suitability for future PrEP intervention studies (e.g., prevalence of renal insufficiency, hepatitis B virus (HBV) infection, hepatitis C virus (HCV) infection, etc.).
- To identify demographic, behavioral, socioeconomic, and psychosocial factors related to: (1) PrEP uptake and PrEP adherence over time, (2) PrEP persistence, and (3) interest in future HIV research, including research involving injectable and implantable agents for PrEP among HIV-uninfected TGW.
- To assess use of medically-prescribed and non-prescription gender-affirming interventions, including exogenous hormones, soft tissue fillers/silicone, and feminizing surgeries (e.g., breast augmentation, vaginoplasty/labiaplasty, orchectomy, etc.).

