### **4.1 Inclusion Criteria**

TGW (assigned male at birth, trans-feminine spectrum – as defined in the SSP Manual – by self-report) who meet all of the following criteria are eligible for inclusion in this study.

1. Eighteen years or older at the time of screening.
2. Willing and able to provide informed consent for the study.
3. Interest in PrEP – as defined in the SSP Manual.

4. Non-reactive HIV test results at Screening and Enrollment.
5. Available to return for all study visits and within site catchment area, as defined per site's Standard Operating Procedures (SOP).
6. At risk for sexually acquiring HIV infection based on self-report of at least one of the following:
  - a) Any anal or vaginal sex with one or more serodiscordant or HIV-unknown serostatus sexual partners in the previous 3 months, regardless of condom use.
  - b) Anal or vaginal sex in exchange for money, food, shelter, or other goods or favors in the previous 3 months.
  - c) History of STI(s) in the past 6 months.
7. Willing to undergo all required study procedures.
8. General good health, as evidenced by the following laboratory values:
  - a) Calculated creatinine clearance  $\geq$  60 mL/minute using the Cockcroft-Gault equation.
  - b) Alanine aminotransferase (ALT) and aspartate aminotransferase (AST)  $<$  2.5 times the upper limit of normal (ULN.)
  - c) HBV surface antigen (HBsAg) negative.

*Note: Otherwise eligible participants with laboratory results outside the above-mentioned values, with the exception of those with reactive HIV test, can be re-tested during the screening window. Participants with reactive HIV tests will not be able to rescreen.*

*Note: Participants who practice receptive vaginal sex cannot be provided Descovy® as it is not approved for this indication.*

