#### **8.2.2 Secondary Endpoints**

Consistent with the secondary study objectives of determining annual incidence of HIV infection, the following endpoint will be assessed:

- Number of documented incident HIV infections during follow-up.

Consistent with the secondary study objectives of determining baseline prevalence and annual incidence of STIs (gonorrhea [GC], chlamydia [CT], and syphilis) and to examine changes in STI incidence over time by study arm, the following endpoint(s) will be assessed:

- Prevalence of STI infection (GC, CT, syphilis) at baseline.
- Incidence of STI infection (GC, CT, syphilis) during follow-up.

Consistent with the secondary study objective of examining changes in sexual risk-taking behavior (e.g., number of serodiscordant or HIV-unknown serostatus sexual partners; number of condomless anal/vaginal sex episodes with these partners):

- Sexual risk-taking behaviors (e.g., number of serodiscordant or HIV-unknown serostatus sexual partners; number of condomless anal/vaginal sex episodes with these partners) measured by ACASI assessments at enrollment and quarterly through Week 78.

Consistent with the secondary study objective of evaluating the cohort's suitability for future PrEP intervention studies (e.g., prevalence of renal insufficiency, hepatitis B virus (HBV) infection, hepatitis C virus (HCV) infection, etc.), the following endpoint(s) will be assessed:

- Baseline laboratory data on all participants.

Consistent with the secondary study objective to identify demographic, behavioral, socioeconomic, and psychosocial factors related to: (1) PrEP uptake and PrEP adherence over time, (2) PrEP persistence, and (3) interest in future HIV research, including research involving injectable and implantable agents for PrEP among HIV-uninfected TGW:

- Individual-level qualitative interview data on a subset of participants addressing core reasons for initiating, discontinuing and/or refusing PrEP.
- ACASI data addressing core reasons for initiating, discontinuing and/or refusing PrEP.
- Interest in future HIV research, collected at Enrollment and Weeks 26, 52, and 78.
- Additional demographic, behavioral, socioeconomic, and psychosocial characteristics collected at Enrollment and quarterly through Week 78.

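### Sexual-risk change is shown from Enrollment with no arm comparison, although entry is selected in part on the same behaviour, so a fall could be regression to the mean

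*Combined protocol and SAP*

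**What the plan says.** The secondary objective in Section 2.2 is "To examine changes in sexual risk-taking behavior". It does not mention study arm, whereas the STI objective just before it does.

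Section 8.2.2 gives as examples of the endpoint "number of serodiscordant or HIV-unknown serostatus sexual partners; number of condomless anal/vaginal sex episodes with these partners". ACASI collects them at the Enrollment Visit and then every quarter, the last time at Week 78.

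The analysis, in Section 8.6.2 under Sexual risk-taking behavior, has two sentences. The first promises exploratory statistics on the ACASI data. The second is "Summary plots will be produced for longitudinal changes in sexual risk-taking behavior among study participants". The neighbouring paragraphs on HIV infections and STIs name both a model and a breakdown by arm.

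Eligibility criterion 6 in Section 4.1 reads "At risk for sexually acquiring HIV infection based on self-report of at least one of the following". Route 6a is "Any anal or vaginal sex with one or more serodiscordant or HIV-unknown serostatus sexual partners in the previous 3 months, regardless of condom use". Route 6b is exchange sex in the previous 3 months, and route 6c is an STI in the past 6 months. Section 6.2 allows at most 30 days from screening to Enrollment.

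**The concern.** If people enter because a fluctuating behaviour was recently present, its later values are lower on average even when nobody changes. Route 6a selects on the construct that the first sexual-risk measure counts. If the Enrollment ACASI looks back over about the same period, the baseline carries that selection and later visits largely do not.

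The plan describes change over time and names no comparator. Both arms are offered PrEP and risk-reduction counselling from the start, and both receive the intervention after Week 26, so a curve over time has no untreated reference. A fall could be credited to PrEP, counselling or navigation when selection produced it, or it could mask a real rise in risk. The randomised comparison up to Week 26, which would remove the selection component in expectation, is not specified for this endpoint.

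**Working it through.** The plan states no figure for this endpoint, so there is nothing to reproduce. The sample size (262, raised to about 310) concerns PrEP adherence and is unaffected.

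**1. Overlap of the two periods.** Criterion 6a looks back 3 months, taken as 91 days. The ACASI recall for sexual behaviour is not stated; 91 days is assumed. With a gap of g days between screening and Enrollment, the shared fraction is (91 − g)/91:
- g = 30: 61/91 = 67%
- g = 7: 84/91 = 92%

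A Week 13 visit on its target day (Day 91, Table 6) looks back to Enrollment and shares nothing with the entry period.

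**2. Model with no effect (all inputs assumed).** Each person has a constant rate. Counts are Poisson within person, and rates are gamma between persons with mean m per 91 days before selection and shape k. A share q qualifies by 6b or 6c regardless of 6a, independently of the partner count. Write P(L) = (k/(k + mL))^k for the probability of no such partner in L × 91 days. Then:
- share admitted: S = 1 − (1 − q)P(1)
- Week 13 mean: W = [m − (1 − q)P(1)·km/(k + m)]/S
- Enrollment mean: E = (1 − g/91)·m/S + (g/91)·W
- share with any such partner at Enrollment: 1 − [P(1) − (1 − q)P(1 + g/91)]/S
- the same share at Week 13: 1 − [P(1) − (1 − q)P(2)]/S

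**3. The largest case in the range (m = 1, k = 3, q = 0.3, g = 7).**
- P(1) = (3/4)³ = 0.4219; P(98/91) = 0.3984; P(2) = (3/5)³ = 0.2160
- S = 1 − 0.7 × 0.4219 = 0.7047
- W = (1 − 0.7 × 0.4219 × 0.75)/0.7047 = 1.105
- E = (84/91) × 1/0.7047 + (7/91) × 1.105 = 1.395
- Change in mean: 1.105/1.395 − 1 = −21%
- Share at Enrollment: 1 − (0.4219 − 0.7 × 0.3984)/0.7047 = 0.797
- Share at Week 13: 1 − (0.4219 − 0.7 × 0.2160)/0.7047 = 0.616, a fall of 18 points

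**4. The range.** Simulated values from the same model:

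| m | k | q | g | Mean, Enrollment to Week 13 | Share with any such partner |
|---|---|---|---|---|---|
| 1 | 3 | 0.3 | 7 | 1.395 to 1.105 (−21%) | 0.797 to 0.616 |
| 1 | 3 | 0.6 | 30 | 1.154 to 1.053 (−8.8%) | 0.654 to 0.597 |
| 3 | 1 | 0.6 | 30 | 3.306 to 3.247 (−1.8%) | 0.811 to 0.786 |
| 6 | 3 | 0.9 | 30 | 6.019 to 6.016 (about 0) | 0.965 to 0.964 |

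Over m = 1 to 6, k = 0.3 to 3, q = 0.3 to 0.9 and g = 7 or 30, the fall is about 0 to 21% in the mean and about 0 to 18 points in the share. If everyone had to meet 6a (q = 0), it would be about 0.8% to 30% and 1 to 32 points. That is not the entry rule.

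**5. Effect on the arm contrast.** Criterion 6 is applied before randomisation, so the expected artefact D is the same in both arms: (change in Immediate + D) − (change in Deferred + D) leaves only the difference in change. Services differ between arms only in the first 6 months (Section 3.1), so this contrast is available at Weeks 13 and 26.

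**The case against.** The case on the other side is substantial.

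- **Entry does not force a high baseline.** A reader might infer that the criteria require everyone to start high on the endpoint. They do not. Someone with no such partner can enter by 6b or 6c, and the 6a threshold of one partner excludes only zeros. This stands, and it is why the lower end of the range is near zero.
- **Condomless episodes are not a criterion.** This is true, since 6a applies whatever the condom use. But the endpoint counts episodes with these same partners, so anyone without such a partner scores zero. Selection on episodes is indirect.
- **The instruments differ.** Appendix Ia has ACASI from Enrollment, not at Screening, and the recall period is unstated. This weakens any numerical claim. It does not remove the selection, provided both reports reflect the same recent behaviour.
- **The text does not say that arms will be pooled.** Section 8.6.2 is silent on arm, and Section 8.6 leaves technical detail to a separate SAP. Display by arm is not ruled out. It is also not planned, although the adjacent analyses do plan it.
- **The analysis is descriptive.** No test, error rate or sample size depends on it, and nothing says a fall will be credited to the intervention. This limits the weight of the point. The objective is nevertheless change itself, and the planned display cannot separate change from selection.
- **Starting the trend at Week 13 would be a poor remedy.** It would discard the only pre-intervention value. Navigation in the Immediate arm begins at Enrollment and PrEP is offered to both arms then, so early behaviour change would be hidden. This objection stands in full.

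**Conclusion.** The point holds in a limited form. Entry is selected in part on recent sexual risk, change is shown from a visit at most 30 days after screening, and no arm comparison is named. A fall after Enrollment could therefore partly or wholly be regression to the mean, and it cannot be attributed to PrEP, counselling or the intervention.

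The expected direction with no effect is downward. The size is not determined: about 0 to 18 percentage points in the share with any such partner, and about 0 to 21% in the mean count. These figures rest on the assumed gamma-Poisson counts, a 3-month ACASI recall, constant personal rates, other routes independent of the partner count, and separate partners in separate periods. Partners who continue across periods would shrink the artefact. A reader might conclude that risk is certain to appear to fall by a material amount; the documents do not support that.

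This is a worthwhile improvement to a secondary, descriptive analysis. The primary comparisons are not affected.

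**What to change.** In Section 8.6.2, or in the separate SAP:

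- Present each sexual-risk measure by arm at every visit, with Enrollment kept as the baseline.
- Add a between-arm comparison at Weeks 13 and 26, adjusted for the Enrollment value and site: for example, a negative binomial model for counts and a logistic model for any such partner.
- Label it as secondary or exploratory, and as a test of co-location and navigation. Both arms are offered PrEP, so it does not test the effect of PrEP on risk behaviour.
- State that within-arm change from Enrollment may include regression to the mean arising from criterion 6.
- State the ACASI recall period for these items.

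The cost is one extra model per behaviour, a few more exploratory comparisons, and some SAP wording. All the data are already scheduled for collection.

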### Baseline laboratory data

Descriptive statistics will be obtained to summarize all baseline variables. Logistic regression models will be used for estimating prevalence of baseline conditions.

### Reasons HIV-uninfected TGW choose to initiate or refuse PrEP

Descriptive summaries, and exploratory statistics will be used to explore patterns in reasons for refusing PrEP. Reasons for PrEP initiation and/or refusal obtained from qualitative interview data will be listed and compared to quantitative data. Logistic regression will be used for assessing associations between assumed characteristics and PrEP refusal.

### Determinants of PrEP uptake, adherence and persistence, and interest in future HIV research

Descriptive summaries, and exploratory statistics will be used to explore patterns in factors affecting interest in PrEP uptake, PrEP adherence, and future HIV research. Regression models will be used to explore associations.

### Use of gender-affirming hormone therapy

For each study visit, GAHT uptake will be defined as the proportion of TGW who initiate GAHT at any time up to and including that given visit among all TGW enrolled in the trial. At each quarterly visit, the proportion of TGW adherent to GAHT is defined as the proportion of enrolled TGW at that study visit who self-report taking 80% of prescribed doses of GAHT. GAHT persistence is defined as the average of each participant's mean number of visits adherent to GAHT as prescribed.

## 8.6.3 Exploratory Analysis

The data analysis plan is described below for each exploratory endpoint defined in Section 8.2.3.

### Perceived drug-hormone interactions

Descriptive summaries, and exploratory statistics will be used to summarize data and explore patterns among self-reported perceptions about drug interactions between AUC agents and

gender-affirming hormonal therapy. Longitudinal regression models will be used to assess changes over time.

#### Experience in intervention trial

Descriptive summaries, and exploratory statistics will be used to summarize data and explore patterns among quantitative data. Qualitative sub-study data analyses will be conducted on an ongoing basis alongside data collection.

#### Secondary laboratory assessments

Summary plots and descriptive tables of local laboratory values will be generated for baseline values and for values measured during the course of the study by treatment arm and visit. For each local laboratory measure, summary statistics will be presented by treatment arm and timepoint, as well as changes from baseline.

#### Discontinuation due to adverse events

The number and percentage of participants who discontinue study product administration and who terminate the study early will be tabulated by reason, grade and treatment arm. For any reasonably common AEs ( $> \sim 20$  events), exploratory analyses will be conducted to assess correlates of the AE, including demographics and duration and patterns of PrEP use, within the limits imposed by the small expected number of events.

### **8.6.4 Missing Data**

Missing outcome data is a threat to the validity of treatment effect estimates in randomized controlled trials. To achieve unbiased statistical estimation and inferences using methods outlined in this protocol, missing data need to be missing completely at random (MCAR). MCAR assumes that missingness does not depend on any observed or unobserved data. When missingness is negligible, statistical methods based on the MCAR assumption can be used with limited impact on the analysis. When the frequency of missing data is more substantial, methods that require the MCAR assumption may give misleading results. In this situation, statistical methods will be performed based on appropriate modeling assumptions and adjusted using weighting methods, or combined with imputation, under the assumption that the data are missing at random (MAR). MAR assumes that the probability of an observation being missing only depends on the observed responses or covariates. Thus, this assumption is less stringent than the MCAR assumption. Weighting adjustments and imputation methods are valid under MAR. We will consider including any of the available baseline predictors of the missing outcomes as covariates in statistical models.

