### ***Selection of Immediate Versus Six-Month Deferred Randomized Trial Design***

Randomized clinical trials are considered the most rigorous of study designs. By randomizing participants to immediate versus deferred access to the intervention (i.e., multi-component, co-located services), the trial will be able to compare differences in outcomes between participants who receive the intervention and those who have not yet received the intervention. By allowing access to the intervention after six months, the study responds to consistent input from community consultations with more than 50 TGW at the five study sites that any delay lasting longer than six months would be unacceptable and negatively impact recruitment into the study and retention of participants in the deferred arm.

In addition to the strong community rationale, the current literature on PrEP discontinuation supports the validity of a six-month deferred arm. In a study of 663 MSM and TGW PrEP initiators in Boston, being a TGW was significantly associated with PrEP discontinuation, and the median time to first discontinuation (of seven days or more) was four months. Data from TGW in Brazil found 8% missed the week 4 visit, 8% missed the week 8 visit, and 16% missed the 24-week visit. The proportion missing the week 24 visit was the same at the end of study visit (week 48), suggesting that participants who discontinue PrEP do so by 24 weeks. Among 1086 veterans initiating PrEP via the Veterans Hospital Administration, the median time to PrEP discontinuation (based on 120 day gap in TDF/FTC possession) was 124 days (4 months). In a study among MSM in 3 US cities, PrEP discontinuation was 27% at 3 months and 40% at final 6-month study visit. In short, the literature supports the expectation that we would see a difference between the deferred and intervention arms by six months. Because participants may elect to start PrEP up until week 39 (the last visit before the end of the first year of the study), we will continue to follow participants for another year to assess the impact of the intervention on PrEP persistence.

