### **8.2 Endpoints**

#### **8.2.1 Primary Endpoints**

Consistent with the primary study objective to assess acceptability and feasibility of delivering integrated HIV prevention services co-located with gender-affirming hormone therapy (GAHT) and PHN using SBCM for TGW, the following endpoints will be assessed:

- Number of participants accepting co-located GAHT services at baseline and subsequent quarterly study visits.
- Number of participants who report desire for co-located services at the end of the study.
- Number of participants retained at Weeks 26, 52 and 78 per study arm.
- Number and content (tracking a participant vs. engagement with a participant) of Peer Health Navigator contacts (text message, email, phone, in-person).

Consistent with the primary study objectives to assess PrEP adherence and persistence for HIV-uninfected TGW in the Immediate Intervention Arm vs HIV-uninfected TGW in the Deferred Intervention Arm, the following congruent endpoints will be assessed:

- Time to PrEP initiation as documented in study eCRFs.
- TFV-DP and FTC-TP levels in DBS measured at quarterly follow up visits after PrEP initiation.
- Drug not dispensed among those who initiate PrEP.
- Self-reported adherence to daily PrEP.
- Time to first PrEP discontinuation

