### **8.6.1 Primary Analyses**

Study arms will be compared for baseline characteristics using descriptive statistics.

For each study visit, PrEP uptake will be defined as the proportion of TGW who initiate PrEP at any time up to and including that given visit among all TGW enrolled in the trial. PrEP uptake will be compared between study arms at the end of Week 26 for the primary objective. Confidence limits will be computed using the binomial distribution.

At each quarterly visit, the proportion of TGW adherent to PrEP is defined as the proportion of enrolled TGW who have confirmed protective levels of PrEP in their blood at that study visit. PrEP adherence (using either TDF or TAF-based regimens) will be **assessed objectively** using thresholds established by recently completed DOT studies. TGW who are missing drug level assessments, and who do not have drug dispensed at their most recent visit will be defined as non-adherent at that visit. The proportion of TGW determined to be adherent at Week 26 will be compared between the two study arms for the primary objective. Confidence limits will be computed using the binomial distribution.

PrEP persistence is defined as the average of each participant's mean number of visits adherent to daily PrEP. The mean number of visits adherent to daily PrEP will be (i) zero for TGW who never initiate PrEP during the study and (ii) the proportion of visits where the participant was confirmed to have protective levels of PrEP (using either TDF or TAF-based regimens) in blood according to objective thresholds established by recently completed DOT studies. PrEP persistence will be compared between study arms.

To assess acceptability in future use of the study intervention, the percentage (with 95% CI) of participants who report an interest in future use of co-located GAHT and peer-delivered health navigation model for HIV prevention in the future will be calculated among those enrolled in each study arm.

Descriptive summaries will be used to summarize and assess different aspects of feasibility such as recruitment, retention, and frequency and content of Peer Health Navigator contacts (text message, email, phone, in-person).

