The proportion of individuals on each of the two PrEP agents (Truvada® vs Descovy®) will be reported at baseline, 13- and 26-week visits. If a significant imbalance is detected between arms at any of these visits, the primary analysis will be adjusted for PrEP agent using regression and/or causal inference methods. Similar strategies will also be employed if differential missingness is observed in each of the primary endpoints between the two arms.

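### For the missing-at-random adjustment of Week 26 adherence, Section 8.6.4 names only baseline predictors and not the Week 13 drug level, which can leave bias of either sign in the arm difference

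*Combined protocol and SAP*

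**What the plan says.** Section 8.6.1 sets the primary adherence comparison: "The proportion of TGW determined to be adherent at Week 26 will be compared between the two study arms for the primary objective". Adherence means a protective drug level at the visit, with enrolled participants as the denominator. One rule fills in some missing results: "TGW who are missing drug level assessments, and who do not have drug dispensed at their most recent visit will be defined as non-adherent". If missingness differs by arm, "Similar strategies will also be employed if differential missingness is observed in each of the primary endpoints between the two arms"; the strategies referred to are regression and/or causal inference methods, with no covariates listed for missingness.

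Section 8.6.4 reserves simple methods for negligible missingness and otherwise turns to weighting or imputation under MAR. It defines the assumption broadly: "MAR assumes that the probability of an observation being missing only depends on the observed responses or covariates". It then closes with the one sentence on model content: "We will consider including any of the available baseline predictors of the missing outcomes as covariates in statistical models". No variable list is given for the weighting or imputation model.

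The intermediate measurement exists. Section 8.2.1 lists "TFV-DP and FTC-TP levels in DBS measured at quarterly follow up visits after PrEP initiation" as a primary endpoint, and Appendix Ia schedules a dried blood spot at Week 13 for everyone.

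**The concern.** An MAR analysis is only as credible as the variables it conditions on. The protocol's own design rationale (Section 1.2) takes missed visits in a Brazilian cohort as a marker of stopping PrEP, "suggesting that participants who discontinue PrEP do so by 24 weeks". On that reading, whether the Week 26 sample exists is related to the outcome, and baseline characteristics alone are unlikely to explain the link.

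The rule in Section 8.6.1 deals with part of this, because participants with no level and no drug dispensed are counted as non-adherent. Those left to the MAR model are therefore the ones who had drug dispensed. This group differs from the whole arm in two ways that pull in opposite directions. Having drug in hand makes them more likely to be adherent than the arm average. A low Week 13 level, if that is what led to dropout, makes them less likely. A baseline-only model sees neither. At stake is the arm difference for the outcome on which the trial was sized.

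**Working it through.** **1. The plan's own figures.** Inputs from Sections 8.3 and 8.4: rates 0.40 and 0.60 (0.5 ∓ d/2, d = 0.20), two-sided alpha 0.05, power 90%, 1:1 allocation, 85% retention.
- Pooled-variance formula: n per arm = [1.96·√(2·0.5·0.5) + 1.2816·√(0.24 + 0.24)]² / 0.20² = 129.3, so 130.
- With variance 0.25 in both arms: (1.96 + 1.2816)²·0.5 / 0.04 = 131.3, matching the stated 131 per arm (262).
- 262 / 0.85 = 308.2, so 309; about 310 is stated.
- SE of the difference at 131 per arm = √(0.24/131 + 0.24/131) = 0.061.

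These figures reproduce, and the present point does not change them.

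**2. Who is left for the MAR model** (taking the most recent visit to mean the last one attended):
- Level missing, nothing dispensed: non-adherent by rule.
- Level missing, dispensed at Week 13: unclassified, but attended Week 13 and has a scheduled sample there.
- Level missing, dispensed at Enrollment, Week 13 missed: unclassified, with no Week 13 level.

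**3. Upper illustration, ignoring the rule.** Assumed: P(adherent at Week 26) is 0.8 if protective at Week 13 and 0.1 if not, and baseline carries no information. The share p protective at Week 13 is 0.714 (Immediate) and 0.429 (Deferred), giving true rates of 60% and 40%. Missingness is 10% throughout in Immediate; in Deferred it is 5% if protective and 25% if not.
- Deferred estimate = (0.429·0.95·0.8 + 0.571·0.75·0.1) / (0.429·0.95 + 0.571·0.75) = 0.441.
- Difference = 60.0 − 44.1 = 15.9 points.
- With 10% and 20% missing in Deferred instead: 18.0 points.
- With 5% and 25% in both arms: 19.1 points.

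**4. With the rule applied.** Let u be the share of an arm with no drug dispensed, taken as truly non-adherent and always classified. Among the rest, P are protective at Week 13 and L are not, with P + L = 1 − u and 0.8P + 0.1L equal to the true rate. If m1 and m0 are the missing fractions in P and L, the baseline-only estimate is

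[0.8·P·(1 − m1) + 0.1·L·(1 − m0)] / [1 − P·m1 − L·m0].

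Solving for P and L:
- Immediate: u = 0.10 gives 0.729 and 0.171; u = 0.20 gives 0.743 and 0.057.
- Deferred: u = 0.15 gives 0.450 and 0.400; u = 0.40 gives 0.486 and 0.114.

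| u Imm. / Def. | Missing Imm. (m1, m0) | Missing Def. (m1, m0) | Imm. | Def. | Difference |
|---|---|---|---|---|---|
| 0.10 / 0.15 | 10%, 10% | 5%, 40% | 59.3 | 44.8 | 14.6 |
| 0.10 / 0.15 | 10%, 10% | 5%, 25% | 59.3 | 42.4 | 16.9 |
| 0.20 / 0.40 | 10%, 10% | 5%, 25% | 58.7 | 39.9 | 18.8 |
| 0.10 / 0.15 | 10%, 10% | 15%, 15% | 59.3 | 39.0 | 20.4 |
| 0.20 / 0.40 | 5%, 5% | 20%, 20% | 59.4 | 36.4 | 23.0 |

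First row, Deferred: (0.8·0.45·0.95 + 0.1·0.40·0.60) / (1 − 0.0225 − 0.16) = 0.366 / 0.8175 = 0.448. Immediate: 0.54 / 0.91 = 0.593. (Differences are taken before rounding.)

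A second way to apply the rule keeps the step 3 pattern and assumes that 30%, 50% or 70% of those not protective at Week 13 had nothing dispensed. The missing ones among them enter the denominator as non-adherent. The difference is then 17.5, 18.4 or 19.3 points, a loss of 2.5, 1.6 or 0.7.

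**5. Conditioning on Week 13 level and dispensing.** Each stratum recovers its own rate. For Deferred in the first row, 0.8·0.45 + 0.1·0.40 + 0·0.15 = 0.40, and the difference returns to 20. This holds by construction: it needs MAR given those variables and a Week 13 level for everyone left unclassified.

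**The case against.** The strongest reply is that no baseline-only model is prescribed. The quoted sentence is permissive and concerns covariates in statistical models. The plan's definition of MAR admits observed responses, and a Week 13 level is one. Section 8.6 defers technical detail to a separate SAP that is not among the documents reviewed, so its imputation model may include Week 13. All of this stands, and it rules out saying that the plan discards Week 13 data. It does not remove the gap: a definition of MAR is not a model specification, and baseline predictors are the only ones named.

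Dispensing is also already used, through the rule in Section 8.6.1, so the step 3 figures overstate the problem. If the most recent visit means the missed Week 26 visit itself, almost nobody remains unclassified. The plan does not say which meaning applies.

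A reader might infer that the fallback estimate is bound to be biased, or that it shrinks the intervention effect because navigators in the Immediate arm follow up missed appointments (Table 3). The documents support neither. Nothing in them shows that the Week 13 level predicts dropout; the evidence in Section 1.2 concerns discontinuation and missed visits in other cohorts. Section 4.5 lists Peer Navigator contact as a retention measure without limiting it to one arm. The bias is zero if missingness is unrelated to Week 13 level and dispensing, and the table shows both signs.

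Finally, a Week 13 level cannot help for participants dispensed at Enrollment who then miss both Week 13 and Week 26. In the Brazilian data cited in Section 1.2, 8% had already missed week 8, against 16% at week 24, so this group may not be small.

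**Conclusion.** The point holds as a gap in specification with a practical remedy. Section 8.6.4 names only baseline predictors for a fallback that may well be needed at the planned 15% attrition, and it leaves out a scheduled measurement that is probably the best predictor of the outcome.

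With the rule in Section 8.6.1 applied, the assumed scenarios run from 5.4 points of shrinkage (14.6 against 20) to 3.0 points of inflation (23.0), and many fall between 0 and 2.5 points. Against an SE of 6.1 points, 2.5 points is about 0.4 SE and 5.4 points about 0.9 SE. These sizes rest on an assumed Week 13 to Week 26 association (0.8 and 0.1), assumed undispensed shares, assumed missingness patterns by arm and uninformative baseline covariates. The documents supply none of these. The conclusion is that a baseline-only adjustment can leave bias, of a sign not known in advance; it is not that the primary estimate is biased.

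**What to change.** Replace the last sentence of Section 8.6.4, or add to the SAP before outcome data are examined by arm, wording to this effect:

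> After the non-adherent rule of Section 8.6.1 has been applied, weighting or imputation models for Week 26 adherence will be fitted separately by arm and will include Week 13 attendance, Week 13 TFV-DP category where available, PrEP initiation and dispensing through Week 13, PrEP agent, site and baseline predictors.

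Three additions complete it:
- Define the most recent visit in the Section 8.6.1 rule, since this decides who is left for the model.
- State how participants with no Week 13 level are handled, for example as a separate category through the attendance indicator or by imputing Week 13 and Week 26 in sequence.
- Add one delta-adjusted (tipping-point) analysis that lowers the odds of adherence among those still missing. It matters most for participants with no Week 13 level.

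The cost is a slightly larger model and one more sensitivity analysis. There is no added participant burden and no change to the sample size. Section 10.2.3 allows drug testing on only a subset of samples, but the quarterly adherence and persistence definitions in Section 8.6.1 already need these levels.
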